7.2.4.2. Manual Muscle Testing-8 Muscle Groups (MMT-8)

This tool assesses muscle strength using manual muscle testing. A 0 to 10-point scale is proposed for use. An abbreviated group of 8 proximal, distal, and axial muscles (neck flexors, deltoids,

biceps brachii, gluteus maximus, gluteus medius, quadriceps, wrist extensors, ankle dorsiflexors) performs similarly to a total of 24 muscle groups, and this abbreviated group is also proposed for use for research studies ([Rider 2010](#); [Rider 2011](#)).

7.2.4.3. Myositis Disease Activity Assessment Tool (MDAAT)

This tool measures the degree of disease activity of extramuscular organ systems and muscle. This is a combined tool that includes the Myositis Disease Activity Assessment Visual Analogue Scales (MYOACT), which is a series of physician's assessments of disease activity of various organ systems modified from the Vasculitis Activity Index, ([Whiting-O'Keefe 1999](#)) and the Myositis Intention to Treat Activity Index (MITAX), which is modified from the British Isles Lupus Assessment Group approach to assess disease activity in SLE ([Hay 1993](#)). The MITAX is composed of a series of organ-specific questions relating to the presence or absence of the clinical feature and the degree of treatment needed for it (intention to treat) ([Rider 2011](#); [Sultan 2008](#)).

7.2.4.4. Physician Global Assessment of Disease Activity (MDGA)

This tool measures the global evaluation by the treating physician of the overall disease activity of the patient at the time of assessment using a 10 cm visual analog scale (VAS) and a 5-point Likert scale ([Rider 2011](#)).

7.2.4.5. Physician Global Impression of Change (MDGIC)

The MDGIC consists of 1 item taken from the Clinical Global Impressions scale (CGI), which was published in 1976 by the US National Institute of Mental Health. Answers are based on a 7-point Likert scale ranging from very much improved to very much worse, asking regarding the patient's overall status ([Guy 1976](#)).

7.2.4.6. Functional Index-2 (FI-2)

The FI-2 is a functional outcome developed for patients with adult PM or DM, assessing muscle endurance in 7 muscle groups. Each muscle group is scored as the number of correctly performed repetitions with 60 or 120 maximal number of repetitions (depending on muscle group). The FI-2 is a further development of the original FI, where redundant tasks were eliminated and the number of repetitions for each task were increased to avoid ceiling effects. It has been validated as to content and construct validity and intra- and interrater reliability. The FI-2 can be performed on just the dominant side, which takes approximately 21 minutes. ([Alexanderson 2006](#); [Rider 2011](#))

7.2.4.7. Functional Assessment: Sit-to-Stand Test (STS)

The STS test score is the number of times that the patient rises to a full stand from the seated position with arms folded across the chest within 30 seconds ([Agarwal 2006](#)). The STS test will be used as a functional assessment for this study.

7.2.4.8. Myositis Damage Index (MDI)

The MDI is a tool that assesses the degree of disease damage of all organ systems. It is composed of a series of organ-specific questions relating to the presence or absence of a given sign or symptom or problem to measure the extent of damage, and an overall rating of the disease damage of each system using a 10 cm VAS to measure the severity of damage (Rider 2011; Sultan 2011).

7.2.4.9. Cutaneous Dermatomyositis Disease Area and Severity Index (CDASI)

The CDASI will be performed only for those patients with DM.

The CDASI is a clinician-scored single-page instrument that separately measures activity and damage in the skin of DM patients for use in clinical practice or clinical/therapeutic studies. The modified CDASI (Version 2) is the one in current use. The modified CDASI has 3 activity measures (erythema, scale, and erosion/ulceration) and 2 damage measures (poikiloderma and calcinosis) which are assessed over 15 body areas. In addition, Gottron's papules on the hands are evaluated both for activity and damage. Lastly, the activity of periungual changes and alopecia is assessed (Rider 2011; Yassaee 2010).

7.2.5. Patient Reported Outcome Measures

The patient-reported outcome measures (PROMs) outlined in the sections that follow will be assessed in this study. For visits at which PROMs are performed, it is recommended that they be completed prior to any other assessments or procedures. All PROMs will be completed by the patient or a designee on a tablet, mobile phone, or other electronic device, with the exception of the EQ-5D-5L, which is a paper-based assessment.

Websites for the individual assessments (where available) are provided in [Section 13.2](#) (Appendix B).

7.2.5.1. Patient Global Assessment of Disease Activity (PtGADA)

The PtGADA is a tool that measures the global evaluation of the patient's overall disease activity at the time of assessment using a 10 cm VAS (Rider 2011).

7.2.5.2. Health Assessment Questionnaire-Disability Index (HAQ-DI)

The HAQ-DI is a tool to assess physical function in myositis (Rider 2011).

7.2.5.3. Patient Global Impression of Change (PGIC)

The PGIC is the PROM counterpart to the CGI, which was published in 1976 by the US National Institute of Mental Health. It consists of one item taken from the CGI and adapted to the patient. Answers are based on a 7-point Likert scale ranging from very much improved to very much worse, asking regarding the patient's overall status (Guy 1976).

7.2.5.4. EuroQoL 5-dimension 5-level (EQ-5D-5L)

EQ-5D-5L is a standardized instrument developed by the EuroQoL Group as a measure of health-related quality of life that can be used in a wide range of health conditions and treatments. The EQ-5D-5L consists of a descriptive system and the EuroQol visual analog scale (EQ-VAS).

The descriptive system comprises 5 levels of severity for each of 5 dimensions (ie, mobility, self-care, usual activities, pain/discomfort, and anxiety/depression). The EQ-VAS records the patient's self-rated health on a vertical VAS. This can be used as a quantitative measure of health outcome that reflects the patient's own judgment. The scores on these 5 dimensions can be presented as a health profile or converted to a single summary index number (utility) reflecting preferability compared to other health profiles.

7.2.5.5. Patient Global Assessment of Disease Damage (PtGADD)

The PtGADD is a tool that measures the global evaluation of the patient's overall disease damage at the time of assessment using a 10 cm VAS.

7.2.5.6. Peak Pruritus Numerical Rating Scale (NRS)

In a study of patients with DM, 50% reported moderate-to-severe itch, which was correlated with increased cutaneous severity (Kim 2018). The Peak Pruritus NRS, used to evaluate itch in atopic dermatitis, will be utilized to evaluate the severity of itch in patients with DM. The Peak Pruritus NRS ranges from 0 to 10, with 0 representing no itch and 10 representing the worst itch imaginable during the worst moment within a 24-hour recall period.

7.2.6. Safety Assessments

Safety will be assessed throughout the study by monitoring of vital signs, physical examinations, and laboratory tests; and by recording and analyzing all AEs and SAEs.

7.2.6.1. Vital Sign Measurements

Blood pressure, pulse rate, and temperature will be measured at the visits shown in the Schedules of Assessments (Table 1 and Table 2). Blood pressure and pulse rate should be collected after the patient has had at least 5 minutes of rest in the seated position. If the blood pressure is elevated on the first measurement at screening and baseline, it should be repeated after at least an additional 5 minutes of rest. It is recommended that blood pressure is measured using the same arm at each assessment. When the time of vital signs measurement coincides with a blood sample collection, the vital signs will be measured before blood sample collection.

7.2.6.2. Weight

When possible, body weight will be recorded at the on-site visits shown in the Schedule of Assessments (Table 1). Body weight, with the patient wearing light clothing and the shoes and jacket or coat removed, will be measured and recorded in kilograms.

For telehealth visits, weight will not be measured; a weight from any source other than the study site should not be recorded.

7.2.6.3. Physical Examination

Complete physical examinations will be performed at the on-site visits specified on the Schedule of Assessments ([Table 1](#)). A complete physical examination should include assessments of at least the following systems: general appearance, head, ears, eyes, nose and throat, neck, dermatological, respiratory, cardiovascular, abdomen, extremities, neurological, musculoskeletal.

At other visits (including other on-site visits and unscheduled visits), a limited physical examination may be performed as directed by the patient complaints and the clinical judgment of the Investigator. Medically significant changes from physical examination will be recorded as AEs. Muscle evaluation findings captured in the muscle assessment instruments will not be recorded unless they are classifiable as SAEs, as per [Section 9.2.1](#).

Limited physical examinations will be performed at telehealth visits.

7.2.6.4. Clinical Laboratory Assessments

Clinical laboratory tests for safety, including hematology, clinical chemistry, immunoglobulins, and clinical laboratory assessments for efficacy measures will be performed at a central laboratory at the visits shown on the Schedules of Assessment ([Table 1](#)).

Hematology: complete blood count with differential.

Clinical chemistry: chemistry panel including electrolytes, AST, ALT, and total bilirubin; aldolase, LDH, CK, and C-reactive protein (CRP).

Additional blood will be sent for biomarker studies as per [Section 7.2.7](#).

Unscheduled or additional laboratory samples may be collected and analyzed by local laboratories if immediate results are necessary for management of TEAEs or dosing determination. Urine pregnancy tests will be performed locally.

Unless otherwise noted, when scheduled simultaneously with a dosing visit, samples for laboratory evaluations should be collected prior to administration of KZR-616.

Clinical laboratory results the Investigator deems clinically significantly abnormal should be repeated within 48 to 72 hours from when the result became available, when possible.

7.2.6.5. Muscle Enzymes

Muscle enzymes (aldolase, ALT, AST, CK, and LDH) will be measured as per [Section 7.2.6.4](#).

7.2.7. Exploratory Biomarkers

Additional blood and serum will be sent for biomarker studies. Detailed instructions for sample collection, processing, storage and shipment will be provided in the Laboratory Manual.

7.2.7.1. Cytokines and Proteomics

Blood samples will be collected at the times shown in the Schedule of Assessments ([Table 1](#)) for the measurement of cytokines by enzyme-linked immunosorbent assay (ELISA). Additional information regarding sample collection and handling are outlined in the Laboratory Manual.

7.2.7.2. Gene Expression

Gene expression (ribonucleic acid [RNA]) profiling may be assessed in blood samples. A whole blood sample will be collected for gene expression analysis for storage and analysis at a later date as specified in the Schedule of Assessments ([Table 1](#)) and to the extent permitted by the national and/or local laws and regulations.

Samples will be used to conduct retrospective disease or population genetic research as a separate analysis not included in this study. Samples may be used to investigate variable response to KZR-616 and to investigate genetic or epigenetic variants thought to play a role in the diseases under investigation in this study. Assessment of variable response may include evaluation of AEs or differences in efficacy. The results may be reported in the separate report.

Additional information regarding sample collection and handling are outlined in the Laboratory Manual.

7.2.8. Contraception Requirements and Pregnancy Testing

Women of childbearing potential must have a negative urine pregnancy test before doses of KZR-616 outlined in [Table 1](#) and [Table 2](#), and must agree to use highly effective and medically acceptable methods of contraception to prevent pregnancy during the study and for 4 weeks after administration of the last dose of KZR-616. For the purposes of this study, WOCBP are defined as postpubescent female patients, unless the patient is postmenopausal (defined by amenorrhea for at least 2 years or amenorrhea for at least 1 year with confirmatory FSH level in the postmenopausal range, as documented historically or measured by the central or local laboratory and if patient is not on supplementary hormonal therapy) or surgically sterile (ie, tubal ligation, hysterectomy, bilateral salpingoophorectomy).

Highly effective contraception is defined as the use of an intrauterine device or hormonal contraceptives (eg, implant or oral) or having a vasectomized partner. In regions where it is considered highly effective contraception, 2 barrier methods (eg, female diaphragm and male condom OR 1 barrier method with spermicide) may be used.

If using a hormonal form of contraception, use must have been stable for at least 4 weeks prior to the Week 1 Day 1 Visit, and if using concomitant mycophenolate, the patient must use another highly effective nonhormonal form of contraception. Abstinence will be acceptable only if it is in line with the preferred and usual lifestyle of the patient. Periodic abstinence (eg, calendar, ovulation) and withdrawal are not acceptable methods of contraception.

For WOCBP, urine pregnancy testing will be performed at the time points shown in [Table 1](#) and [Table 2](#). KZR-616 should not be administered prior to confirmation of a negative test at visits at which pregnancy tests are performed. Positive urine pregnancy tests should be confirmed by a serum pregnancy test.

Samples for FSH testing may be collected at any time during the study to confirm postmenopausal status in female patients whose childbearing potential status has changed since the Screening Visit of Study KZR-616-003. Only after confirmation of postmenopausal status is pregnancy testing not required.

Male patients must continue to use an effective contraception method (eg, condom with spermicide) for 1 week following the last dose of KZR-616 or be congenitally or surgically sterile (eg, vasectomy with documented confirmation of post-surgical aspermia). The decrease in male contraception use from 12 weeks in prior KZR-616 protocols to 1 week in Study KZR-616-003E is supported by the short half-life of KZR-616 (<2 hours), full recovery of immunoproteasome inhibition within 3 days of dosing, lack of mutagenic potential as determined in vitro and in vivo nonclinical studies, and lack of reproductive organ findings in the 6- and 9-month rodent and monkey repeat-dose toxicity studies. Additionally, no teratogenic effects were found in the definitive embryofetal toxicity studies in rats and rabbits. As per International Council for Harmonisation (ICH) M3 guidance, lack of reproductive and teratogenic findings in general toxicity and embryofetal toxicity studies is sufficient to support the treatment of male patients in Phase 1 and 2 trials prior to conducting fertility studies.

8. STUDY DISCONTINUATION

The Investigator must make every reasonable effort to keep each patient on study for the duration of the study, including through the safety follow-up, lost to follow-up, consent withdrawal, or end of study, whichever occurs first (see [Section 8.2](#) for additional details).

8.1. Study and Individual Patient Stopping Rules

8.1.1. Study Stopping Rules

If any of the following events occur, administration of KZR-616 will be temporarily discontinued until a thorough review of the accumulated safety data is undertaken by the Data Monitoring Committee (DMC) (or appropriate alternative):

- Death in any patient, unless the cause of death is due to obvious alternative etiology
- Unexpected life-threatening event in any patient, unless due to obvious alternative etiology
- Three or more of the same Grade 3 or higher AE (judged by the Investigator, Medical Monitor, or Sponsor's representative), occurring in 20% or more individuals, unless due to obvious alternative etiology
- Any event of thrombotic microangiopathy, thrombocytopenic purpura, or hemolytic uremic syndrome
- Any event that, in the opinion of the Medical Monitor, DMC (or appropriate alternative), or Sponsor, contraindicates further dosing of additional patients

8.1.2. Individual Patient Stopping Rules

If any of the following events occur, administration of KZR-616 to an individual patient should be discontinued until a review of the accumulated safety data is undertaken by the DMC (or appropriate alternative):

- Any event that fulfills criteria for a study stopping rule, unless due to an obvious alternative etiology (see [Section 8.1.1](#))
- Any event that, in the opinion of the Investigator, Medical Monitor, DMC (or appropriate alternative), or Sponsor, contraindicates further dosing

After such a review, resumption of dosing may be considered at the same or lower dose including consideration for any prophylactic interventions (eg, as per [Section 6.1.2](#))

8.2. Early Withdrawal of Patients from the Study

Patients must be withdrawn from the study for any of the following reasons:

- Patient request/informed consent withdrawn due to an AE
- Patient request/informed consent withdrawn for any reason other than an AE
- Patient becomes pregnant
- AE (whether or not related to KZR-616) that precludes further participation in the study, in the judgment of the Investigator and/or Sponsor
- Any event of thrombotic microangiopathy, thrombocytopenic purpura, or hemolytic uremic syndrome

Patients may be withdrawn from the study for any of the following reasons:

- Protocol non-compliance, in the judgment of the Investigator and/or Sponsor
- Lost to follow-up
- The Investigator or Sponsor considers that it is in the patient's best interest not to continue participation in the study
- Administrative decision by the Investigator or Sponsor

Patients are free to withdraw from the study at any time without providing reason(s) for withdrawal and without prejudice to further treatment. The reason(s) for withdrawal will be documented in the eCRF. If a patient withdraws consent, all samples obtained will be retained for analysis unless the patient confirms that he or she wishes the samples to be discarded.

Patients withdrawing from study treatment will be encouraged to complete the ETV within 14 days and return for an EOS Visit approximately 12 weeks after receipt of their last dose of KZR-616 to complete the final evaluations according to this protocol, particularly safety evaluations. The aim is to record data in the same way as for patients who complete the study.

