6.1.3.2. Missed Doses

Doses should be administered within the visit windows as per the Schedule of Assessments ([Section 7.1](#)). Any doses administered outside of the visit window will be considered a protocol deviation; however, if necessary to avoid missing a dose, doses may be administered up to 3 days from the date of scheduled administration with a minimum of 4 days required between doses.

Patients who meet individual patient stopping rules ([Section 8.1.2](#)) may resume dosing after discussion between the Investigator and Medical Monitor. Upon resumption of dosing, subsequent doses should be timed according to the original dosing schedule based on Day 1. Missed doses should be documented in the eCRF as per [Section 9.1.4](#). Patients who are discontinued for missed doses should have their discontinuation recorded in the eCRF based on the reason the doses were missed, eg, AE, protocol noncompliance (see [Section 8.2](#)).

If KZR-616 is permanently discontinued due to an AE, the planned assessments (see Schedule of Assessments in [Table 1](#)) should continue for the protocol-specified time period. If the patient cannot continue with the planned assessments, the Early Termination Visit (ETV) should be accomplished at a minimum (see [Section 8.2](#)).

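### For thrombotic microangiopathy, Section 8.2 mandates leaving the study while other sections call only for stopping the drug and continuing assessments; the effect is small and the wording fix is cheap

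*Combined protocol and SAP*

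**What the plan says.** Four parts of the protocol bear on a patient with thrombotic microangiopathy, thrombocytopenic purpura or hemolytic uremic syndrome (TMA/TTP/HUS below).

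- **Section 8.2** opens with "Patients must be withdrawn from the study for any of the following reasons" and lists "Any event of thrombotic microangiopathy, thrombocytopenic purpura, or hemolytic uremic syndrome". The same list has a separate, judgment-based entry: "AE (whether or not related to KZR-616) that precludes further participation in the study, in the judgment of the Investigator and/or Sponsor".
- **Section 9.5.1.2** says to interrupt KZR-616 on suspicion, to allow resumption if the diagnosis is excluded, and to stop the drug permanently if it is confirmed. It then refers to Section 8.2. It does not itself ask for withdrawal from the study.
- **Section 6.1.3.2** says: "If KZR-616 is permanently discontinued due to an AE, the planned assessments" in Table 1 "should continue for the protocol-specified time period". It makes no exception for TMA/TTP/HUS. Its fallback is: "If the patient cannot continue with the planned assessments, the Early Termination Visit (ETV) should be accomplished at a minimum".
- **Section 8** places a duty on the investigator to make every reasonable effort to retain each patient, safety follow-up included.

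On visits after withdrawal, Section 8.2 says "Patients withdrawing from study treatment will be encouraged to complete the ETV within 14 days" and applies the same encouragement to an End of Study (EOS) Visit about 12 weeks after the last dose. It adds: "The aim is to record data in the same way as for patients who complete the study". Section 8.4 is firmer on the Early Termination Visit (ETV): it should happen within 14 days of withdrawal, if possible, with the Table 1 procedures.

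**The concern.** A confirmed TMA/TTP/HUS event triggers two instructions that cannot both be followed literally: remove the patient from the study, and continue the planned assessments. Stopping the drug protects the patient. The protocol gives no reason why leaving follow-up would add protection. Section 8.2 also moves from withdrawal from the study in its list to withdrawal from study treatment in its closing paragraph, which suggests that the two were merged rather than deliberately equated.

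Long-term safety is one of the two objectives (Section 2.1). Thrombotic microangiopathy is one of the two named adverse events of special interest (Section 9.5.1), and one event pauses dosing study-wide pending review (Section 8.1.1). Table 1 places hematology, chemistry, vital signs and a physical examination at both the ETV and the EOS Visit. Per Section 7.2.6.4 these laboratory tests include a complete blood count, bilirubin and LDH, which bear on the anemia and thrombocytopenia that Section 9.5.1.2 describes. With at most 24 patients, the course of a single case would matter to the safety account.

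**Working it through.** The plan has no figure of its own to reproduce here: the study is descriptive and has no sample size calculation. The check is a reading of the rules side by side and a count of visits.

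**1. Do the rules conflict for a patient able and willing to stay?**
Section 6.1.3.2 is triggered by permanent discontinuation for an adverse event, which Section 9.5.1.2 requires on a confirmed diagnosis. Its fallback covers a patient who cannot continue. Section 8.2 already handles patients whose adverse event precludes participation through its judgment-based entry. The TMA/TTP/HUS entry therefore has separate effect only for patients not judged unable to continue. For them, the sections disagree.

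**2. How firm is each visit after withdrawal?**
- ETV: should be done at a minimum (6.1.3.2); should take place if possible (8.4); encouraged (8.2).
- EOS: encouraged (8.2). Section 3.1 describes it as part of the general design but does not address withdrawn patients.

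Neither is required after withdrawal. The EOS Visit is the softer of the two.

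**3. Visits scheduled if off-drug follow-up ends at EOS**
This is the only off-drug duration that the protocol states: 12 × 7 = 84 days after the last dose.
- Table 1 treatment visits fall on Days 78, 162, 246, 330, 414, 498, 582 and 666, each 84 days apart. EOS after a full course is 666 + 84 = Day 750, as in Table 1.
- For a last dose on day *d* (1 to 665), count the Table 1 treatment visits later than *d* and no later than *d* + 84. Because the spacing is 84 days, the count is exactly 1. Example: *d* = 134 (Week 20) gives the range Day 135 to Day 218, which contains only Day 162.
- Section 6.1.3.2: 1 treatment visit + EOS = 2. The two coincide only for *d* = 78, 162, 246, 330, 414, 498 or 582 (7 of 665 days), which leaves 1.
- Section 8.2: ETV + EOS = 2.
- Difference in scheduled duration: 84 − 84 = 0 days.

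**4. Visits scheduled if Section 6.1.3.2 means the full Table 1 schedule**
Section 6.1.3.2 does not define its period for a patient off drug, so this is an alternative assumption. It takes a patient on the 96-week schedule.
- Last dose on Day 1: 9 post-baseline visits against 2, a gap of 7.
- Last dose about Week 20: Weeks 24, 36, 48, 60, 72, 84, 96 and 108 = 8 against 2, a gap of 6.
- Last dose at Week 95: Weeks 96 and 108 = 2 against 2, a gap of 0.

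For a patient whose dosing would have ended at Week 48, a last dose about Week 20 leaves Weeks 24, 36 and 48 plus EOS at Week 48 + 12 = 60. That is 4 against 2, a gap of 2.

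**5. Adverse event collection if EOS is missed**
Section 9.1.5 collects adverse events until the later of 30 days after the last dose or the EOS Visit.
- EOS attended: about day 84.
- EOS not attended, read literally: day 30.
- Difference: 84 − 30 = 54 days.

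**The case against.** The strongest reply is that the sections can be reconciled and that little is lost.

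- Sections 9.5.1.2 and 6.1.3.2 both point to 8.2, so 8.2 could be taken as the specific rule and the withdrawn patient as one who cannot continue. This is a possible reading, but it leaves the TMA/TTP/HUS entry redundant beside the precluding-event entry, and it leaves EOS merely encouraged.
- Sections 8 and 8.3 impose real duties to retain and trace patients, and 8.2 aims for the same data as from completers. These points stand and show the intent. They sit awkwardly with a mandatory instruction to withdraw.
- For an acute event, an ETV within 14 days may serve better than the next Table 1 visit, which can be up to 84 days away. This stands, and it is a reason to keep the ETV in the fix.
- The 54-day figure needs the patient to miss EOS, which could happen under any wording. This stands. It is a conditional worst case, not an expected loss.

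A reader might also infer that both post-withdrawal visits are only encouraged. The documents do not support that for the ETV, because 6.1.3.2 and 8.4 both say it should be done.

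Nor do they support an inference that the event's own safety data would be lost. It is reported within 24 hours (9.5.1) and followed until resolved, stabilized or chronic (9.1.5). If it is serious, laboratory results and hospital records can be requested, and related serious events remain reportable after 30 days (9.2.2). Unscheduled visits may include any Week 24 procedure (7.1.1).

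**Conclusion.** The inconsistency is real, and its consequence is small. As written, Section 8.2 removes from the study a patient with TMA/TTP/HUS who may be able and willing to stay, although the other sections require only that the drug be stopped and that assessments continue. What is exposed is scheduled follow-up, chiefly the EOS Visit and the collection of new adverse events up to it.

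If off-drug follow-up ends at EOS, the two rules schedule about two visits each over the same 84 days, and the difference lies in how firmly attendance is asked for. A claim that months of visits are lost would need Section 6.1.3.2 to mean the full Table 1 schedule, which the protocol does not say. The shortening of routine adverse event collection by about 54 days assumes that EOS is missed and that Section 9.1.5 is read literally.

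No hypothesis test is affected, since none is planned. The event may never occur: Section 9.5.1.2 describes cases only with nonspecific proteasome inhibitors. This is a cheap improvement to consider, not a flaw that undermines the study.

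**What to change.** In Section 8.2, take confirmed TMA/TTP/HUS off the list of reasons for mandatory study withdrawal and make it a reason for mandatory permanent discontinuation of KZR-616, in line with Section 9.5.1.2. Keep the patient on study. Require the ETV within 14 days and the EOS Visit 12 weeks after the last dose, unless consent is withdrawn. In Section 6.1.3.2, it would help to state when follow-up ends for a patient off drug, for example at that EOS Visit.

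Leave the drug-stopping rules, the entry for adverse events that preclude participation and the pregnancy rule as they are.

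The cost is a wording change and two already defined visits for a rare patient. Patients may still leave at any time, so the change cannot guarantee attendance.
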